4.2 Intervention

I. Initial Phase of Study: Intervention For Primary Endpoint.

Romiplostim, n=60.

All patients will begin weekly romiplostim at 2 mcg/kg, subcutaneously. The romiplostim dose will be titrated as per Section 9.0, based on weekly CBC/platelet counts. For titration purposes, the target platelet count is 150,000-200,000/mcL.

II. Maintenance romiplostim, During Resumed Chemotherapy/Secondary Efficacy Endpoint

All patients on romiplostim who achieve a platelet count adequate (>100,000/mcL) and resume chemotherapy will be followed with continuation of weekly, titrated romiplostim.

In patients whose platelet counts have recovered within three weeks, we are observing for ability to resume 2 cycles (or eight weeks, whichever comes first) of cytotoxic chemotherapy without recurrence of chemotherapy-induced thrombocytopenia leading to chemotherapy dose delay or reduction; change in chemotherapy for progression of disease or other cancer related conditions; change in chemotherapy for other toxicities unrelated to thrombocytopenia; and death due to all causes. The duration for patients off chemotherapy will be noted. In addition we are also censoring patients who have tolerated chemotherapy with romiplostim support for up to 12 months.

Patients who are benefitting from the romiplostim, will be able to remain on treatment beyond the completion of 12 months on study, at the discretion of their oncologist and the study participating hematologist.

5.0 THERAPEUTIC/DIAGNOSTIC AGENTS

Romiplostim, a member of the TPO mimetic class, is an Fc-peptide fusion protein (peptibody) that activates intracellular transcriptional pathways leading to increased platelet production via the TPO receptor (also known as cMpl). The peptibody molecule contains two identical single-chain subunits, each consisting of human immunoglobulin lgG1 Fc domain, covalently linked at the C-terminus to a peptide containing two thrombopoietin receptor-binding domains. Romiplostim has no amino acid sequence homology to endogenous TPO. Romiplostim is produced by recombinant DNA technology in *Escherichia coli (E coli)*.

Romiplostim is approximately 59 kilodalton and is comprised of 4 Mpl-binding domains and an Fc fragment. The peptibody is produced by recombinant DNA technology in Escherichia coli (E coli). Though it has no amino acid sequence homology to endogenous thrombopoietin (eTPO), romiplostim is an agonist of the thrombopoietin (TPO) receptor and signals and activates intracellular transcriptional pathways to increase platelet production.

Romiplostim is supplied as a sterile, preservative-free lyophilized white powder ready for reconstitution. It is supplied for single use in 5 cc Type I glass vials containing 625 μ g of romiplostim, 500 μ g deliverable drug product. When reconstituted with the appropriate volume of sWFI, romiplostim is at a concentration of 0.5 mg/mL in 10 mM histidine, 4% (w/v) mannitol, 2% (w/v) sucrose, and 0.004% (w/v) polysorbate 20 at a pH of 5.0. The product, when reconstituted, is a clear colorless solution practically free from particles.

Prior to administration, romiplostim is reconstituted in the vial to 0.5 mg/mL (1.2 ml of sWFI is added to vials containing 625 μ g (500 μ g) of romiplostim), and drawn into a syringe for subcutaneous injection.

Romiplostim vials will be stored in their carton to protect from light until the time of use. Keep romiplostim vials refrigerated at 2°to 8°C (36° to 46°F). Do not freeze.

- A. Romiplostim is an FDA approved drug, approved for the indication of chronic immune (idiopathic) thrombocytopenic purpura (ITP). The investigators Brochure, provided by Amgen, is attached as Appendix C. The product insert is also provided as Appendix B.
- B. Relevant statements from the Product Insert:
 - INDICATIONS AND USAGE: "Romiplostim is a thrombopoietin receptor agonist indicated for the treatment of thrombocytopenia in patients with chronic immune thrombocytopenia (ITP) who have had an insufficient response to corticosteroids, immunoglobulins, or splenectomy."

6.0 CRITERIAFOR SUBJECT ELIGIBILITY

6.1 Subject Inclusion Criteria

- 1. Patients (18 years of age or greater) with active non-hematological cancer:
 - A. The patients have previously received a chemotherapy regimen including one or more of the following agents:
 - 1. Nucleoside Analogue, including gemcitabine and fluorouracil
 - 2. Carboplatin or cisplatin
 - 3. Anthracycline
 - 4. Alkylating agent
 - 5. Other chemotherapy agents with thrombocytopenia as known common toxicity.
- 2. Patients who have not had any cytotoxic chemotherapy within 14 days of beginning the study.
- 3. Thrombocytopenia:
 - A. Defined as platelet count <100,000/mcL.
 - B. The patient will have had at least 2 CBCs with platelet counts <100,000/mcL separated by at least 4 weeks, and no platelet count ≥100,000/mcL in the prior 6 week period, despite (1) delay or (2) modification of chemotherapeutic regimen.
 - C. A platelet count of >100,000/mcL, that follows within 7 days of a platelet transfusion, will not make the patient ineligible, as long as one or more subsequent platelet counts confirms thrombocytopenia (<100,000/mcL).

- D. Patients have undergone bone marrow aspirate and biopsy, or peripheral blood test in the prior 3 months, without evidence of leukemia or myelodysplasia by fluorescent in situ-hybridization (FISH).
- E. Dysplastic changes, based on morphology only, will not exclude the patient if FISH panel for MDS is normal.
- 4. KPS > 50 or ECOG performance status <2.
- 5. Ability to provide written informed consent.

6.2 Subject Exclusion Criteria

- Patients with history of hematologic malignancies, including leukemia, myeloma, myeloproliferative disease, lymphoma, or myelodysplastic diseases. Romiplostim has been associated with transient increases in immature blood cell counts and a higher risk for progression to acute myeloid leukemia in Myelodysplastic Syndrome patients treated with Nplate.
- 2. Patients with known bone metastases, with evidence of corticol bone damage/lytric lesions/blastic lesions on standard imaging studies (CT/MR).
- 3. Anemia (Hgb <8.0 gm/dl) or leukopenia (absolute neutrophil count (ANC) <1,000/mcL). Use of red cell transfusions, erythropoietin, or G-CSF, as ordered by the managing oncology service, is acceptable and does not preclude participation.
- 4. Patients with underlying liver disease, such as cirrhosis or chronic hepatitis, and do not have primary or metastatic cancer in the liver will be excluded if ALT/AST >3X ULN or Total Bili >3X ULN. In the presence of primary or metastatic liver cancer, patients will be excluded if ALT/AST >5X ULN or Total Bili >5X ULN.
- 5. Patients with a history of a prior symptomatic venous thrombotic event such as DVT or pulmonary embolism and symptomatic arterial thrombotic events such as myocardial infarction, ischemic cerebral vascular accident or transient ischemic attack will be ineligible if they have not tolerated anticoagulation therapy. If patients remain on anticoagulation, or have completed the prescribed course of anticoagulation, they will be eligible for enrollment. A venous thrombotic event associated with a central venous catheter will not make the patient ineligible.
- 6. Serious concomitant medical condition that could interfere with the conduct of the clinical trial, such as unstable angina, renal failure requiring hemodialysis, or active infection requiring IV antibiotics
- 7. Pregnant women/lactating mothers
- 8. Patients unwilling to use contraception.

7.0 RECRUITMENT PLAN

This study will be conducted at MSKCC and participating institutions. Potential research subjects will be identified by members of the solid tumor oncology services. Fortunately, this will be based on existing referral patterns to the Hematology Service.

After the consultation and results of the cytogenetics and FISH, if a patient qualifies for the trial, the consulting hematologist will discuss the possibility of participation in the study. If consent is offered, the risks: benefits will be presented to the patient by an investigator prior to the patient consenting. If the patient consents, they will be enrolled by a study RSA (see section 15.1). Similar recruitment procedures will be followed at participating institutions.

This study does not compete with any existing or planned other studies for CIT and therefore, we anticipate a high percent of the appropriate patients will be referred. It is expected that a total of 60 patients will be recruited to this study.

8.0 PRETREATMENT EVALUATION

Documentation of tests resulted and/or verification will be completed within the following guidelines before enrolling on trial

Within 28 days prior to enrollment:

- Hematologic consultation with an institutional hematologist.
- Record current medications
- Physical examination

Within 48 hours prior to enrollment:

- CBC with peripheral smear (must have 2 tests) (CBC must include: WBC, Hgb, platelet, MCV, cell differential.)
- Comprehensive Metabolic Panel (also referred to as a Comprehensive Chemistry Panel (CCP))
 (must include: BUN, Creatinine, sodium, potassium, chloride, CO2, calcium, glucose, total
 Bilirubin, total protein, albumin, alkaline phosphatase, AST, ALT)
- LDH
- PT
- aPTT
- Negative pregnancy test (serum hCG or urine) result in women of child bearing potential.

Prior to enrollment:

- CT or MRI performed within the prior 60 days of enrollment indicating active cancer or
- Positive serum marker within the prior 30 days of enrollment.

Within 90 days prior to enrollment:

- Bone marrow aspirate and biopsy, or peripheral blood test
 - FISH panel does not indicate MDS
 - Morphology and FISH does not indicate leukemia

9.0 TREATMENT/INTERVENTION PLAN

- I. Initial Phase of Study: Intervention For Primary Endpoint. Romiplostim, n=60.
 - A. Patients will begin weekly romiplostim treatment at 2 mcg/kg, subcutaneously.
 - B. Weekly CBC, comprehensive chemistry panel, LDH, PT, and aPTT will be performed, (as well as monitoring laboratory tests) for the first 3 weeks on treatment.
 - The romiplostim dose will be titrated by a study investigator.
 - The target platelet count for romiplostim dose titration is 150,000/mcL. A platelet count of ≥100,000/mcL is the threshold for successful response and the range of acceptable platelet

counts is 100-200k/mcL. These target platelet values have been used by investigators since the opening of this trial. Language specifying exact values was added in Amendment 16.

In the initial 3 successive weeks, the weekly romiplostim dose will be increased by 1 mcg/kg, until the platelet count 100,000-200,000/mcL. With romiplostim dose escalation, if the platelet count reaches ≥100,000/mcL, (adequate to resume chemotherapy), but not ≥150,000/mcL, the dose of romiplostim will not be escalated above 5 mcg/kg.

The dose of romiplostim may be modified at the discretion of the study investigator in consultation with the PI. Smaller dose increment (or decreases) may be needed to titrate the platelet count to the 100,000- 200,000/ mcL target.

C. 3 Week: Primary Endpoint.

The anticipated recovery of the platelets is within 3 weeks of initiation of romiplostim. The initial endpoint will be at 3 weeks.

The proportion of patients who have achieved a platelet count of ≥100,000/mcL within 3 weeks, (adequate to resume chemotherapy) and the weekly absolute platelet counts are recorded.

- II. Maintenance Romiplostim, During Resumed Chemotherapy/Secondary Efficacy Endpoint
 - A. All patients who achieve an adequate platelet count to resume chemotherapy (≥100,000/mcL) and resume chemotherapy will be followed with continuation of weekly, titrated romiplostim. If the patient receives romiplostim therapy for ≥12 months, the scheduling of routine labs and treatment dosing will be at the discretion of the investigator.
 - B. The secondary endpoint will be documented for patients whose platelet counts have recovered within three weeks. We will observe for ability to resume 2 cycles (or eight weeks, whichever comes first) of cytotoxic chemotherapy without recurrence of chemotherapy-induced thrombocytopenia leading to chemotherapy dose delay or reduction; change in chemotherapy for progression of disease or other cancer related conditions; change in chemotherapy for other toxicities unrelated to thrombocytopenia; and death due to all causes. The duration for patients off chemotherapy will be noted. In addition we are also censoring patients who have tolerated chemotherapy with romiplostim support for up to 12 months.
 - C. Romiplostim dose titration. After resumption of full-dose chemotherapy, the romiplostim dose can be further titrated based on platelet count at beginning of each chemotherapy cycle. The dose adjustments are from the prior week's romiplostim dose. The below dose titration refers to the initial 2 cycles of resumed chemotherapy as well as the continuation phase for patients who successfully complete the study through 2 cycles.
 - 1. The target platelet count, at initiation of a cycle of chemotherapy is 100,000-200.000/mcL.
 - 2. If the pre-chemotherapy cycle platelet count is >200,000/mcL, the romiplostim dose will be reduced by 0.5 mcg/kg.
 - 3. If the pre-chemotherapy cycle platelet count is >250,000/mcL, the romiplostim dose will be reduced by 1.0 mcg/kg

- 4. If the pre-chemotherapy cycle platelet count is <100,000/mcL, the romiplostim dose will be increased by 1.0 mcg/kg.
- 5. The dose of romiplostim may be rounded off to the nearest 50 mcg.
- 6. The dose of romiplostim may be modified at the discretion of the study investigator in consultation with the MSKCC P.I. Smaller dose increments (or decreases) may be needed to titrate the platelet count to the 100,000-200,000/mcL target.

III. Discontinuation of Romiplostim.

- A. Discontinuation of Cancer Therapy. After the 3 week period of the initial endpoint is reached, if the treating medical oncologist discontinues chemotherapy or switches to a cancer therapy not associated with thrombocytopenia, the romiplostim may be discontinued.
- B. If a patient develops a Grade 3/4 adverse event, attributable to Romiplostim, based on the Common Terminology Criteria for Adverse Events (CTCAE), the Romiplostim will be discontinued.
- C. If a patient develops a symptomatic deep vein thrombosis and/or pulmonary embolism, not associated with hemodynamic instability, and not considered life-threatening, the romiplostim may be continued if there is consensus of judgment of the treating oncologist and study investigator.

10.0 EVALUATION DURING TREATMENT/INTERVENTION

Patients will come for visits to the study-center/hematologist on a weekly basis during the study. The intervals of the weekly visits will be 7 +/- 2 days. These visits will be for the purpose of monitoring the safety and efficacy of the romiplostim intervention, as well as to allow for further dose titration. Treatment can be held up to 16 days if a patient develops an intercurrent medical illness or symptom that is unrelated to study drug therapy. Treatment may be held up to 20 days if the patient is unavailable for non-medical reasons, such as vacation or travel.

For the first 3 weeks on treatment, patients will receive weekly CBC, COMP, LDH, PT, and aPTT. During consecutive weeks, CBCs will be obtained weekly, for the purpose of monitoring the platelet recovery and to allow for further dose titration. Once per month (30 days +/- 10 days),,comprehensive metabolic panel (see above for itemization), LDH, Prothrombin Time, and activated Partial Thromboplastin Time will be monitored. If at any time the automated hematology analyzer flags possible morphological abnormalities, peripheral smears will be ordered for further analyze in order to monitor the platelet recovery and continue dose titration.

Patients who remain on romiplostim for 4 or more months, will undergo bone marrow aspirate and biopsy, or peripheral blood test, with reticulin stain, cytogenetics, and FISH panel for MDS, in the 30 day period after completion of the 4th month.

Patients will have a CBC performed within 1-4 weeks after the last dose of romiplostim.

11.0 TOXICITIES/SIDE EFFECTS

Based on our initial experience, we have not observed treatment-related toxicities in our first 40+ patients. Based on the romiplostim Prescribing Information, the most common adverse

reactions (≥5% higher patient incidence in romiplostim versus placebo) are arthralgia, dizziness, insomnia, myalgia, pain in extremity, abdominal pain, shoulder pain, dyspepsia, and paresthesia.

Individual cases of thrombosis and been reported in patients receiving romiplostim, but in one recent review of long-term use of romiplostim, "The thrombotic adverse event rate across all studies was 0.09 events per 100 patient-weeks on romiplostim therapy," markedly lower than would expected in patients with active cancer receiving chemotherapy. We have not observed an increased thrombosis rate compared with expected rates in patients with metastatic cancer, on chemotherapy, however, we will monitor any clinical evidence of thrombosis as well as hemorrhage.

Assessment of potential toxicity will be based on the Common Terminology Criteria for Adverse Events (CTCAE) Version 4.0. We will monitor for evidence of marrow toxicity, with weekly CBC (CBC must include: WBC, Hgb, platelet, MCV, cell differential) and lab toxicities of grade 3/4 will be adjudicated on a regular basis by the PI or Co-PI of the study. In addition, cytogenetics testing through bone marrow aspirate or peripheral blood will be performed within 30 days after the completion of the 4th month on treatment.

Patients will be monitored for Adverse Events throughout the study at the following time points: Toxicity Assessments will be completed at 3-weeks from enrollment (3-weeks from initiation of romiplostim in cross-over patients), and every 3 months while on romiplostim. A final toxicity assessment will be completed 1 month after the last dose of romiplostim. However, if the patient is discontinuing chemotherapy and going to hospice/ comfort care, the final toxicity assessment will be omitted if toxicities were managed regularly. For purposes of toxicity assessment, 3 months will be defined as 90 days +/- 15 days, 1 month is defined as 30 days +/- 15 days, and 3 weeks will be defined as 21 days + 9 days.

The study will report only those toxicities that are not known to be linked to the patient's prior chemotherapy treatment or underlying disease. All toxicities meeting this criteria should be reported to MSKCC as an Adverse Event in CRDBi-Multicenter with supporting source documentation.

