Lastly, the frequency of thrombosis, marrow toxicity, and organ dysfunction will be tabulated.

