17.2 Serious Adverse Event (SAE) Reporting

SAE reporting is required as soon as the participant signs consent. SAE reporting is required for 30-days after the participant's last investigational treatment or intervention. Any events that occur after the 30-day period and that are at least possibly related to protocol treatment must be reported.

If an SAE requires submission to the IRB office per IRB SOP RR-408 'Reporting of Serious Adverse Events', the SAE report must be sent to the IRB within 5 calendar days of the event. The IRB requires a Clinical Research Database (CRDB) SAE report be submitted electronically to the SAE Office as follows:

For all other trials: Reports that include a Grade 5 SAE should be sent to [contact]. All other reports should be sent to [contact].

The report should contain the following information:

Fields populated from CRDB:

- Subject's initials
- Medical record number
- Disease/histology (if applicable)
- · Protocol number and title

Data needing to be entered:

- The date the adverse event occurred
- The adverse event
- The grade of the event
- Relationship of the adverse event to the treatment (drug, device, or intervention)
- If the AE was expected
- The severity of the AE
- The intervention
- Detailed text that includes the following

- A explanation of how the AE was handled
- A description of the subject's condition
- Indication if the subject remains on the study
- If an amendment will need to be made to the protocol and/or consent form
- If the SAE is an Unanticipated Problem

The PI's signature and the date it was signed are required on the completed report.

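### The hospice waiver of the one-month post-treatment toxicity assessment may leave non-serious events unrecorded in a group selected by prognosis; a record review would close the gap

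*Combined protocol and SAP*

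**What the plan says.** Section 11.0 sets toxicity assessments at 3 weeks, "every 3 months while on romiplostim", and once after treatment: "A final toxicity assessment will be completed 1 month after the last dose of romiplostim", with one month taken as 30 +/- 15 days. The exception follows directly. For a patient who is stopping chemotherapy and "going to hospice/ comfort care, the final toxicity assessment will be omitted if toxicities were managed regularly". The section does not say what regular management means or who judges it.

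Other safety collection carries no hospice exception:

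- Section 10.0, on treatment: "Patients will come for visits to the study-center/hematologist on a weekly basis during the study".
- Section 10.0, after treatment: "Patients will have a CBC performed within 1-4 weeks after the last dose of romiplostim".
- Section 16.0.3 lists Adverse Event and Laboratory forms at Off Study, in a chart written for participating sites.
- Section 17.2: "SAE reporting is required for 30-days after the participant's last investigational treatment or intervention". For later events: "Any events that occur after the 30-day period and that are at least possibly related to protocol treatment must be reported".

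The safety analysis in Section 14.0 is one sentence: "Lastly, the frequency of thrombosis, marrow toxicity, and organ dysfunction will be tabulated". It gives no time window, no denominator and no handling of patients without a final assessment.

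**The concern.** The waiver depends on prognosis. Patients leaving chemotherapy for comfort care are selected by deterioration, and it is plausible that they have more thrombosis and organ dysfunction than those who stay. The assessment they miss is the only scheduled contact after the last dose whose purpose is to find toxicities. An event that is never looked for cannot enter the table, so any loss runs one way, toward a cleaner profile.

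The safety counts are small. Section 3.4 reports three deep vein thromboses in the first 20 courses and judges this against a historical range of 10% to 30%. With counts of that order, one or two unrecorded events could change how the final table reads.

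**Working it through.** The plan gives no figure for this gap. The operating-characteristics table in Section 14.0 concerns the primary endpoint and plays no part here. The first step is therefore to ask what each remaining safeguard would find in the month after the last dose.

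- **SAE reporting (17.2).** It covers the full 30 days, and the definition in 17.2.1 includes death, life-threatening events, hospitalization and medically important events. Serious thrombosis and organ failure remain reportable. But this is a duty to report, not a scheduled contact, and under 17.3 a site's clock starts when it learns of the event. Section 9.0 foresees symptomatic thrombosis that is not life-threatening. Such an event managed without admission would be an SAE only if it met another criterion, such as medical importance.
- **CBC at 1 to 4 weeks (10.0).** It bears on marrow toxicity. It does not detect thrombosis or hepatic or renal dysfunction, and no chemistry panel is scheduled after the last dose.
- **Off Study forms (16.0.3).** They capture events up to the time they are completed. Under Section 13.0, stopping chemotherapy for a reason other than thrombocytopenia ends treatment, so they may be completed before the month has run. The documents do not fix the timing.
- **Weekly visits and periodic assessments (10.0, 11.0).** These are on-treatment monitoring.
- **The waiver's own condition.** It concerns how known toxicities were handled in the past, so it cannot show that nothing happens in the following 30 days.

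What remains without scheduled ascertainment is non-serious thrombosis and chemistry-based organ dysfunction in that month.

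The second step shows how far any number depends on assumptions. For thrombosis:

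expected missed events = 60 × h × r × (1 − c)

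- 60 is the sample size (Section 14.0).
- h, the share of patients whose assessment is omitted, is assumed to be 0.1 to 0.5.
- c, the share of events caught by SAE reporting, is assumed to be 0, 0.5 or 0.9.
- r, the 30-day risk, is derived in two ways:
  - From the rate in Section 11.0, 0.09 per 100 patient-weeks: r = 1 − exp(−0.0009 × 30/7) = 0.00385.
  - From the 10% to 30% in Section 3.4, assumed to accrue over 12 down to 3 months of 30.4 days: λ = −ln(0.90)/(12 × 30.4) gives r = 1 − exp(−30λ) = 0.0086, and λ = −ln(0.70)/(3 × 30.4) gives r = 0.1107.

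Results:

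| Source of r | c = 0 | c = 0.5 | c = 0.9 |
|---|---|---|---|
| Historical range, h = 0.1, r = 0.0086 | 0.05 | 0.03 | 0.01 |
| Historical range, h = 0.5, r = 0.1107 | 3.32 | 1.66 | 0.33 |

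At the cited romiplostim rate with c = 0, the figure is 60 × 0.1 × 0.00385 = 0.02 to 60 × 0.5 × 0.00385 = 0.12.

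The range runs from almost nothing to about three events. Its top needs the 30% figure to accrue in 3 months, half the patients to be waived and SAE reporting to find nothing. The last of these conflicts with Section 17.2. The formula also assumes that every waived patient survives the 30 days. This is a sensitivity range, not an estimate.

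**The case against.** A reader might infer that post-treatment safety data are simply absent for hospice patients and that the tabulated frequencies are therefore understated. The documents do not support that. The waiver is conditional, 30-day SAE reporting and the post-dose CBC apply to everyone, and the Off Study forms have no hospice exception. Nothing in the documents shows that an event has been or will be lost.

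Nor does the plan say that a patient without a final assessment counts as event-free. Section 14.0 is silent on the point, and silence is not a rule.

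Three further arguments carry weight:

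- The end of Section 11.0 limits reporting, for all patients, to toxicities not known to be linked to prior chemotherapy or the underlying disease. Events known to come from progression would be left out even at a completed assessment. That filter may be a broader source of under-reporting than the waiver, and it limits what restoring the assessment would recover.
- The historical range in Section 3.4 is for patients on chemotherapy, and the rate in Section 11.0 is for time on romiplostim. The waived month is off both, so missing it does not clearly distort either comparison.
- Safety is descriptive, with no test or threshold, and sparing a patient in comfort care a visit is a defensible choice.

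These points limit the size and consequence of the gap. They do not close it. None of the safeguards is a scheduled look for non-serious thrombosis or abnormal chemistry after the last dose, and the attribution filter pushes in the same direction. The burden on the patient, which is the best reason for the waiver, disappears if the assessment is made from the record.

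**Conclusion.** The point holds in a limited form. Section 11.0 drops the only toxicity assessment after treatment for a group defined by prognosis, on a condition that is undefined and looks back. Non-serious thrombosis and organ dysfunction in the following month may go unrecorded in these patients, and the safety frequencies under Section 14.0 may be modestly understated as a result.

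The direction follows from the design, since omission can only remove events. The size cannot be estimated from the documents, and the range shown above rests on assumed values for the waived share, the accrual period and SAE capture. Serious events remain reportable. The primary endpoint and the success rule are unaffected. No stated figure is wrong; this is an improvement worth making because it is cheap.

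**What to change.** In Section 11.0, replace the waiver with a final assessment at 30 +/- 15 days by review of the medical record, or by telephone call where appropriate, with no visit and no blood draw. Apply the same attribution rule as for other patients. This also removes the need to define the condition now attached to the waiver.

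In Section 14.0, show each tabulated safety frequency with the number of patients whose post-treatment assessment was completed.

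The cost is a change of wording in each of the two sections and one record review or call per affected patient, which is a small amount of existing study-staff time. Patients carry no added burden beyond an occasional call.
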